8.1 Efficacy assessments

This is a PK/PD study; therefore, the primary outcome measures are described in Section 8.5 and Section 8.6.

8.1.1 Spirometry

8.1.1.1 General requirements

Lung function (FEV₁) at the study centre will be measured by spirometry using the site's own equipment. Spirometry should be performed by the investigator or authorised delegate according to American Thoracic Society/European Respiratory Society (ATS/ERS) guidelines (Miller et al 2005).

Important! Patients should withhold their bronchodilator medications prior to scheduled spirometry per Section 6.6. The patient's usual asthma medications may be administered following completion of the lung function procedures.

8.1.1.2 Spirometry technique

Patients should avoid engaging in strenuous exertion for at least 30 minutes prior to spirometry measurements. Patients should avoid eating a large meal for at least 2 hours prior to spirometry measurements at the centre. Forced expiratory manoeuvres should be performed with the patient seated in an upright position. If this is not comfortable for the patient, standing is permitted. The same position should be used by the patient for each forced expiratory manoeuvre from enrolment throughout the study. The head must not be tilted during manoeuvres and the thorax should be able to move freely; hence, tight clothing should be loosened. A nose-clip should be used for the manoeuvre. Mouthpieces of the same dimension and shape should be used by the patient from enrolment throughout the study.

The forced expiratory manoeuvre (FEV₁) should start with a maximal inspiration and then followed by a fast and forceful expiration that should last for at least 6 seconds (3 seconds for children aged <10 years). It is important to encourage the patient to continue the expiration to be fast and forceful throughout the manoeuvre. Ensure that none of the following has occurred:

- coughing during the first second
- glottis closure
- leak or
- obstruction of the mouthpiece (by the tongue).

Multiple forced expiratory efforts (at least 3 but no more than 8) will be performed for each center spirometry session and the 2 best efforts that meet the ATS/ERS acceptability and reproducibility criteria will be recorded in the eCRF. The best efforts will be based on the highest FEV₁. The absolute measurement (for FEV₁), and the percentage of predicted normal

value will be recorded using the local spirometer at the site with predicted values derived from the reference value of choice, eg, [Nair et al 2017](#), [NHANES III 2010](#), [Quanjer et al 2012](#), etc.

8.1.2 Clinical outcome assessments

Asthma Control Questionnaire-Interviewer Administered

The Asthma Control Questionnaire (ACQ) is a 7-item assessment comprised of 6 patient-reported items and a single clinical item pertaining to pre-bronchodilator FEV₁ % predicted ([Juniper et al 1999](#)). The ACQ was developed for self-administration by adults and adolescents. Patients are asked to record their experience with 5 symptoms (night-time waking, symptoms on waking, activity limitation, shortness of breath, and wheezing) and use of short-acting β 2 agonist (SABA) over the previous week using a 7-point scale (0 = no impairment; 6 = maximum impairment). The final item pertaining to FEV₁ uses a similar 7-point response scale. Shortened versions of the ACQ can be produced by omitting the FEV₁ item (ACQ-6) or the FEV₁ and SABA items (ACQ-5) from the assessment or scoring ([Wyrwich et al 2011](#)). The ACQ score is calculated by taking the mean of the 7 equally weighted items. The ACQ score range is 0 (well controlled) to 6 (extremely poorly controlled). Individual score change of at least 0.5 is meaningful and is used to support the responder definition ([Juniper et al 2005](#)). Mean ACQ scores ≤ 0.75 indicate well-controlled asthma, scores between 0.75 and ≤ 1.5 indicate partly controlled asthma, and a score >1.5 indicates poorly controlled asthma ([Juniper et al 2006](#)).

An interviewer-administered version of the ACQ, which was developed for use with children aged ≥ 6 years (ACQ-IA), will be used in this study with the omission of item 7. The only difference between the ACQ-IA and the ACQ is the mode of administration. The ACQ-IA is administered by trained individuals according to standardized instructions to help the child understand concepts like “during the last week” and the 7-point scale. Per the assessment instructions, help from parents/caregivers is sought only as a last resort. Thresholds for defining poor asthma control and responder status have been evaluated but not to the extent of the self-administered version for adults and adolescents. The estimated threshold indicating poor asthma control is an ACQ-IA score ≥ 1.25 in patients ages 6 to 17 years ([Nguyen et al 2014](#)). The estimated minimal clinically important difference is 0.5 ([Juniper et al 2010](#), [Nguyen et al 2014](#)).

The questionnaire will be completed at the study centre during every study visit except Visit 3 on Day 1 ([Table 1](#)). This will capture the early onset of effect and the effect of maintenance treatment. Completion of the ACQ-IA may also provide early insight into potential safety concerns.

Patient Global Impression of Change Interviewer Administered

The Patient Global Impression of Change (PGIC) question captures the patient's overall evaluation of response to treatment (Guy 1976). The PGIC is included to assess how a patient perceives their overall change in health status since the start of study treatment(s). This item is useful in characterizing the overall impact of the treatment. The patient is asked to report the degree to which they have changed since entering the treatment period using a 7-point scale ('Much Better', to 'About the same', to 'Much worse'). The patient is instructed to select the one response that gives the most accurate description of his/her state of health (overall status).

An interviewer administered PGIC (PGIC-IA) will be used in this study to help the child understand what is being asked. The PGIC-IA will be administered by trained individuals according to standardized instructions to help the child understand the question and response options. Help from caregivers/parents is sought only as a last resort. The PGIC-IA will be completed at the study centre at Visits 9, 10, 11 and 13 (Table 1).

Clinician Global Impression of Change

The Clinician Global Impression of Change (CGIC) question captures the patient's overall evaluation of response to treatment from the perspective of the clinician (Busner and Targum 2007; Guy 1976). The CGIC is included to assess how the clinician interprets and perceives the patients overall change in health status since the start of study treatment(s). This item is useful in characterizing the overall impact of the treatment from the clinician's perspective. It provides a brief, stand-alone assessment of the clinician's view of the patient's global functioning prior to and after initiating a study medication.

The clinician is asked to report the degree to which they perceive the patient has changed since entering the treatment period using a 7-point scale ('Much Better', to 'About the same', to 'Much worse'). The CGIC will be completed by the clinician at the study centre at Visits 9, 10, 11 and 13 (Table 1).

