3 OBJECTIVES AND ENDPOINTS

Study objectives and endpoints are shown in [Table 2](#).

Table 2 **Study objectives and endpoints**

| Primary objectives: | Endpoints/variables: |
|--|--|
| To evaluate the pharmacokinetics (PK) of benralizumab administered subcutaneously (SC) in children from 6 to 11 years of age with severe eosinophilic asthma | 
 ● Clearance ● Area under concentration time curve to Day 28 (AUC₀₋₂₈) ● Maximum serum concentration (C_{max}) ● Terminal phase elimination half-life (t_{1/2}) ● Time to reach C_{max} (T_{max}) |
| To evaluate the pharmacodynamics (PD) of benralizumab administered SC in children from 6 to 11 years of age with severe eosinophilic asthma | Change from baseline in peripheral blood eosinophil count at Weeks 4, 8, 12 and 16 (Part A), and Weeks 24 and 48 (Part B) |
| Secondary objectives: | Endpoints/variables: |
| To characterize the PK of benralizumab | Body weight-adjusted clearance |
| To evaluate the immunogenicity of benralizumab | Presence of anti-benralizumab antibodies |
| To evaluate the effect of benralizumab on pulmonary function | Change from baseline in pre-dose (when applicable), pre-bronchodilator, FEV ₁ measured at Weeks 4, 8, 12, and 16 (Part A), and Weeks 24 and 48 (Part B) |
| To assess the effect of benralizumab on asthma symptoms and other asthma control metrics | Change from baseline in ACQ-IA score, measured at screening and Weeks 1, 2, 4, 8, 12, and 16 (Part A), and Weeks 24, 32, 40 and 48, and at follow-up (Part B) PGIC-IA, measured at Week 16 (Part A), Weeks 24, 32 and 48 (Part B), and at the DXD/WD visit CGIC, measured at Week 16 (Part A), Weeks 24, 32 and 48 (Part B), and at the DXD/WD visit |
| Safety objective: | Endpoints/variables: |
| To assess the safety and tolerability of benralizumab | AEs Vital signs Collection of clinical chemistry/haematology parameters and urinalysis |
| Exploratory objective: | Endpoints/variables: |
| To evaluate exacerbations experienced | Annualized asthma exacerbation rate (AAER) |

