7.1.1 Procedures for discontinuation of study treatment

A patient that decides to discontinue study treatment will always be asked about the reason(s) and the presence of any AEs. The date of last administration of study treatment should be documented in the eCRF. Patients permanently discontinuing study treatment should be given locally available standard of care therapy, at the discretion of the investigator.

All patients who prematurely discontinue IP should return to the study site and complete the procedures described for the Early Discontinuation (DXD) Visit within 4 weeks after the last dose of IP. At that visit, although no longer on IP, patients should be encouraged to remain in the study. Although only AEs, SAEs, and concomitant medication are required to be collected after the DXD Visit, safety data collection should continue according to the study protocol.

Note that in this case, the DXD Visit replaces the nearest regular visit while the following visits continue as possible. If the patient or guardian does not agree to continue in-person study visit(s), a modified follow-up, such as telephone contact with the patient or guardian, should be arranged to ensure the collection of safety information through the 48-week time point.

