3.1.4 Visit windows

Table 1 of the CSP detailed the time points and visit window for the study assessments. All summaries which are presented by time point will use a visit window to classify the data record, which is derived from the assessment date relative to the reference start date (date of first dose of study treatment). This approach allows appropriate classification of visits which may have occurred significantly earlier or later than the protocol assessment schedule, as well as the use of data captured at visits which have no fixed timing.

Inclusion within the visit window should be based on the actual date and not the intended nominal date of the visit.

Any data collected at unscheduled or repeat visits will be listed, and will be included in baseline definitions (Section 3.1.1), and in any definitions of maximum value, minimum value or last value within the relevant study period.

Data collected at unscheduled or repeat visits will also be included in visit windows, and therefore may be included in summaries by visit. In the case of a missing value at a scheduled visit, which is then followed by a non-missing value at an unscheduled or repeat assessment within the same visit window, the non-missing value at the unscheduled/repeat assessment will replace the missing value at the scheduled visit.

If a subject has more than one non-missing value within the same visit window, the following rules will apply:

- The non-missing value closest to the target day will be selected for analysis at that visit
- If two non-missing values are the same distance from the target day, the earlier of the two values will be selected for analysis at that visit
- If two non-missing values are recorded on the same day and have a different assessment time associated with both of them, the value with the earliest assessment time will be selected for analysis at that visit.
- If two non-missing values are recorded on the same day and have no assessment time associated with at least one of them, or the same assessment time associated with both of them, the average of the two values will be selected for analysis at that visit.
If a subject has no value within a particular visit window, then the subject will have a missing value at that visit in summaries.

Due to the overlap in the week 1 and 2 visit window schedule of assessments the following rules will apply subject to the above rules described in this section above:

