- If Week 1 timepoint has only one record within analysis days 3-10 then this will be assigned to the Week 1 analysis visit, as described above.
- If Week 1 timepoint has multiple records (with evaluable results) within analysis days 3-10 then:

- a) if the latest record (using time) has analysis day = 10, then this record will be considered for selection within the Week 2 analysis visit, subject to the existing rules described in this section above, and
- b) all earlier records within analysis days 3-10 will be considered for selection within the Week 1 analysis visit, subject to the existing rules described in this section above

For PK measures, if there are 2 samples from the same date, the value from the scheduled visit will be used. If the scheduled visit is missing, then the record from the unscheduled visit will be used. If the sampling times are different, both PK samples will be transferred to database and used in population PK (PopPK) analysis.

Blood samples for determination of PK parameters in serum will be taken at timelines as specified in Table 1 of CSP. Blood samples taken at visits when a dose of benralizumab is administered must be taken pre-dose. Blood samples taken at visits when no benralizumab dose is administered may be taken at any time during the day of the visit. The time and date of blood samples taken for PK analysis must be recorded on the eCRF

For PK serum concentration-time data, any post-dose samples taken outside the window from scheduled time point will be excluded from the summary tables and figures.

The adjusted analysis-defined windows will be based on the collection schedule listed in the protocol and variables will be windowed to the closest scheduled visit for that variable.

Visit windows following baseline will be constructed in such a way that the upper limit of the interval falls halfway between the two visits (the lower limit of the first post-baseline visit will be study day 1). If an even number of days exists between two consecutive visits then the upper limit will be taken as the midpoint value minus 1 day. Visit windows are constructed so that every observation collected can be allocated to a visit ([Table 1](#)). No visit windows will be defined for screening visits.

Table 1: Visit windows for assessments

Timepoint Target	Day	Visit Window							

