		AE, CM, Asthma Exac and VS	PK sampling	ACQ-IA	Clinical chemistry, Haematology , Serology, Urinalysis, and FEV1	Brief PE	ADA,	PGIC- IA and CGIC	Height and Weight
Baseline	0	See section 3.1.1 for baseline definitions							
Week 0 day 0									
Week 0 day 1	1	1-2	1-2						
Week 1	7	3-10	3-10	1-10					
Week 2	14	11-20	11-20	11-20					
Week 4	28	21-41	21-41	21-41	1-41	1-41			
Week 8	56	42-69	42-69	42-69	42-69	42-69	1-83		
Week 12	84	70-97	70-97	70-97	70-97	70-97			
Week 16	112	98-139	98-139	98-139	98-139	98-139	84-139	1-139	1-139
Week 24	168	140-195	140-195	140-195	140-251	140-195	140-195	140-195	140-251
Week 32	224	196-251		196-251		196-251		196-279	
Week 40	280	252-307		252-307		≥252			
Week 48	336	308-348	308-348	308-348	≥252		308-348	≥280	≥252
Follow-up (Week 52)	362	≥349		≥349					

Abbreviations: ACQ-IA interviewer-administered asthma control questionnaire, ADA anti-drug antibody(ies), PGIC-IA interviewer administered patient global impression of change, PK pharmacokinetics, VS vital signs, AE adverse events, CM concomitant medication, ACQ-IA interviewer-administered asthma control questionnaire, Exac Asthma exacerbation, PE Physical examination, ECG electrocardiogram.

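### The Week 16 window for PGIC-IA and CGIC opens at Day 1, so ratings made at an early stop visit can be reported as Week 16 ratings

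*Protocol*

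**What the plan says.** SAP 3.1.4 assigns each observation to a visit by its actual date. For every measure, "the lower limit of the first post-baseline visit will be study day 1", and for upper limits, "If an even number of days exists between two consecutive visits then the upper limit will be taken as the midpoint value minus 1 day". Windowing is meant to allow for early and late visits, "as well as the use of data captured at visits which have no fixed timing". Where several values fall in one window, the one closest to the target day is used.

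In SAP Table 1 the first PGIC-IA/CGIC window is Week 16, Days 1-139. At Week 16, ACQ-IA, FEV1 and PK have Days 98-139 and ADA has Days 84-139. Height and weight share the Day 1 opening.

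Protocol Table 2 lists "PGIC-IA, measured at Week 16 (Part A), Weeks 24, 32 and 48 (Part B), and at the DXD/WD visit", and the same for CGIC. Protocol 7.1.1 places the DXD visit within 4 weeks after the last dose and says that "the DXD Visit replaces the nearest regular visit while the following visits continue as possible". After DXD, only AEs, SAEs and concomitant medication are required.

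For ACQ-IA, the SAP Table 1 row reads "Week 1 7 3-10 3-10 1-10"; the last entry, Days 1-10, is the ACQ-IA column. The items are scored "over the previous week using a 7-point scale (0 = no impairment; 6 = maximum impairment", and Visit 4 is Day 7 ±3. Of the ACQ-IA visit schedule, protocol 8.1.2 says: "This will capture the early onset of effect and the effect of maintenance treatment".

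**The concern.** PGIC-IA and CGIC ask how much the child has changed since treatment started, so elapsed time is part of what the answer means. If a rating made at a stop visit on Day 28 is tabulated at Week 16, that row mixes children rated after 16 weeks with children rated much earlier who had already stopped. Early stopping may be linked to poor response or to an adverse event, so the mixing need not be random.

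The row feeds three outputs in SAP 3.3.5 and 4.2.11: the response distribution, the responder percentages (improved, much improved, very much improved) and the patient-clinician agreement percentages. The SAP limits DXD data to one dosing cycle after the last dose for PK concentrations (4.2.5.2) and eosinophils (4.2.6.1). It has no DXD rule for these ratings.

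**Working it through.** **1. Reproduce the plan's windows.** The upper limit is the midpoint of consecutive target days, minus 1 if the midpoint is a whole day and rounded down otherwise. The first window opens at Day 1.

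- PGIC-IA/CGIC targets are Days 112, 168, 224 and 336. (112+168)/2 = 140, giving 139; (168+224)/2 = 196, giving 195; (224+336)/2 = 280, giving 279. The windows are 1-139, 140-195, 196-279 and ≥280, as printed in SAP Table 1.
- ACQ-IA: (7+14)/2 = 10.5, giving 10, so Week 1 is Days 1-10. (84+112)/2 = 98, so Week 12 ends on Day 97 and Week 16 opens on Day 98, as printed.

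The PGIC-IA/CGIC Week 16 window therefore reaches 112 − 1 = 111 days before its target and 139 − 112 = 27 days after. The protocol visit window is ±7 days (Days 105-119).

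**2. Place the stop visits.** Latest DXD day = last-dose day + 28.

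| Last dose | DXD due by | SAP label | Days before target |
|---|---|---|---|
| Day 0 | Day 28 | Week 16 | 84 |
| Day 28 (Week 4) | Day 56 | Week 16 | 56 |
| Day 56 (Week 8) | Day 84 | Week 16 | 28 |

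DXD may be earlier than its due day, so the last column is a minimum at nominal dosing days. A child who stops after the Week 16 dose should already have a Week 16 rating close to Day 112, and the closest-to-target rule keeps that one.

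**3. Does the selection rule remove the problem?** Only if a second rating falls between the stop visit and Day 139. Protocol 7.1.1 does not require one.

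**4. Weight of one child.** In a stratum at the minimum of 8, 1/8 = 12.5 percentage points. With 30 children split evenly, 30/2 = 15 and 1/15 = 6.7 points. SAP 4.1 uses the number of patients in the group as denominator. A stop-visit rating of improved therefore adds that amount to the Week 16 responder percentage. A rating of no change or worse adds it to that category and leaves the responder percentage as it was.

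**5. Would a Day 98 opening exclude these ratings?** Yes, at nominal dosing days (Day 84 at the latest). It also does with the Week 8 dose at the end of its visit window: 56 + 7 + 28 = Day 91, still before Day 98.

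**6. ACQ-IA recall.** Day 0 is the first-dose day (SAP 3.1.2). For a score on Day d, pre-dose share = max(0, 7 − d)/7: 3/7 (43%) on Day 4, 2/7 (29%) on Day 5, 1/7 (14%) on Day 6, and 0 from Day 7. If visits are uniform over Days 4-10, the mean is (3+2+1)/(7×7) = 6/49 = 12%. The Week 2 window opens at Day 11, or Day 10 in the overlap case of SAP 3.1.4, so it has no pre-dose recall.

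**The case against.** The strongest objection is that the documents disagree on whether these ratings are taken at the stop visit at all. Protocol Table 2 and the synopsis say both are. SAP 1.1.2 lists DXD/WD for CGIC only. Protocol 8.1.2 and SAP 3.3.5 name only the scheduled visits or weeks. This stands: if no rating is taken at DXD/WD, the wide window does little harm. It is a reason to reconcile the passages, because the endpoint table as written does collect both.

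A reader might infer that no later rating can ever displace the stop-visit one. That is too strong. Protocol 7.1.1 encourages children to stay and lets later visits continue as possible, so a true Week 16 rating may exist and would be selected. It is simply not required. Nor does the sentence about DXD replacing the nearest visit settle the label: it can be read as governing visit conduct, not tabulation.

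The 12.5-point figure is the smallest-stratum case, and no discontinuation rate is given. Children who withdraw in Part A may be replaced, which enlarges the group. It does not remove the early rating, because the safety analysis set keeps every treated child.

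On ACQ-IA, a reader might infer that the Day 1 opening spoils the Week 1 result. The documents do not support that. Scores on Days 4-6 are in window because Visit 4 is Day 7 ±3. The SAP opening adds only Days 1-3, when no ACQ-IA is scheduled. A Day 4 score would turn a true change of −0.5 into about −0.5 × 4/7 = −0.29 only if the full effect were immediate and recall averaged evenly over days, neither of which is stated. Week 2 still shows early effect free of pre-dose recall.

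**Conclusion.** The point holds for PGIC-IA and CGIC. Under the SAP's own rules, a rating at a stop visit due by about Day 28, 56 or 84 is reported as Week 16, at least 84, 56 or 28 days before the target. Each such child weighs 12.5 points in a stratum of 8 and about 6.7 in one of 15. This rests on three assumptions: ratings are taken at DXD/WD as protocol Table 2 says, doses are given on nominal days, and no later rating falls in the window. How many children would be affected cannot be derived from the documents.

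For ACQ-IA only a note is warranted: a modest overlap of recall with the pre-dose period, averaging about 12% under uniform visit timing, and arising from the protocol visit window.

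All of these endpoints are secondary and descriptive, with no hypothesis tests. Primary PK and PD are not touched.

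**What to change.** - In SAP Table 1, set the PGIC-IA/CGIC Week 16 window to Days 98-139. Add a sentence to SAP 3.1.4 exempting these ratings from the Day 1 opening and from the principle that every observation is allocated to a visit.
- Tabulate DXD/WD ratings in a separate row labelled as at discontinuation, with the study day listed.
- Reconcile protocol Table 2, the synopsis and protocol 8.1.2 with SAP 1.1.2 and 3.3.5 on whether PGIC-IA and CGIC are taken at DXD/WD.
- For ACQ-IA, start the Week 1 window at Day 4 to match the protocol, keep Day 4-6 scores in the row, and footnote the recall overlap. Leave the visit window alone. Restricting the row to Days 7-10 would discard 3 of the 7 permitted visit days, and Visit 4 is shared with PK sampling.

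The cost is a SAP table edit, some programming and slightly fewer values in the Week 16 row. Nothing is lost if the ratings left out of that row are still listed. Protocol 9.5.1 allows SAP amendments until database lock.
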